4. STUDY DESIGN

The study design for this pilot study is a prospective cohort study.

5. STUDY POPULATION

5.1 Population

The study population are patients with ICH that have no family history of hereditary forms of ICH such as hereditary CAA (HCHWA-D) and no cognitive impairment before the ICH. Patients will be aged ≥ 55 y, since the radiological Boston criteria for CAA-related ICH only include patients ≥ 55 y.¹⁸

5.2 Inclusion criteria

ICH patients:

1. Age ≥ 55 y
2. Ability and willingness to provide written informed consent.
3. Supratentorial ICH with CAA^a or HA^b as the most likely cause.

^a CAA-related ICH is defined as an ICH that meets the criteria for definite or probable CAA according to the Modified Boston Criteria (appendix A)

^b HA-related ICH is defined as ICH located in the basal ganglia, thalamus, or the deep white matter and the presence of hypertension defined as: on treatment for hypertension, or known with high blood pressure (two measurements SBP >140 or DBP >90 mmHg) but not treated for hypertension.

5.3 Exclusion criteria

1. Age < 55 y
2. Unable to provide informed consent.
3. Pre-existing cognitive impairment assessed with the Informant Questionnaire on Cognitive Decline in the Elderly (IQCODE); scores between 53 - 63 reflect pre-existing cognitive impairment.¹⁹

4. Contra indications, such as:

Contra-indications for 3T MRI. Examples of possible contra-indications are:

- Claustrophobia
- Pacemakers and defibrillators
- Nerve stimulators
- Intracranial clips
- Intra-orbital or intraocular metallic fragments
- Cochlear implants
- Ferromagnetic implants
- Hydrocephalus pump
- Intra-uterine device
- Permanent make-up
- Tattoos above the shoulders
- Reduced kidney function (estimated GFR < 30 ml/min/1,73m²; or nephrogenic systemic fibrosis / nephrogenic fibrosing nephropathy (NSF/NFD))
- Known prior allergic reaction to gadolinium contrast or one of the constituents of its solution for administration

Contraindications for lumbar puncture:

- Intracranial tumor
- Compressio medullae
- Signs and symptoms of increased intracranial pressure
- Local infections of the skin
- A coagulopathy including use of anti-coagulant drugs (INR ≥ 1.8) or thrombocytopenia (<40)

Use of acetylsalicylic acid, NSAIDs, COX2 inhibitors or prophylactic low-molecular-weight heparin are no contraindications for lumbar puncture,

5.4 Sample size calculations

For this pilot study, we require 32 participants (16 CAA-related ICH and 16 HT-related ICH). This sample size is considered to be sufficient to study the feasibility of the study procedures. Furthermore, the results of a pilot study with this sample size should provide sufficient data that are needed to determine a sample size of a future, larger cohort study.

6. METHODS

6.1 Study parameters/endpoints

Cognitive functioning

The neuropsychological assessment will consist of a battery of tests that measure different cognitive domains. Premorbid cognitive functioning will be assessed with the Informant Questionnaire on Cognitive Decline in the Elderly (IQCODE). Cognitive functioning will be tested using a Mini-Mental State Examination (MMSE), a Montreal Cognitive Assessment (MOCA), a Frontal Assessment Battery (FAB), Digit Span Test (DST), RAVLT-15 words test, Stroop test, Trail making test, the Hospital Anxiety and Depression Scale (HADS), the Center for Epidemiologic Studies Depression Scale (CES-D), the Neuropsychiatric Inventory Questionnaire (NPI-Q), the Starkstein Apathy Scale (SAS) and the Prikkelbaarheidsschaal (PS). Cognitive impairment was defined as a score ≤ 1.5 standard deviation below the general population mean in one or more cognitive domains.

MRI markers

The presence and number of MBs, cSS, WMH, cSAH, ePVS, microinfarcts, intragyral hemorrhages, cortical atrophy and other new and known small vessel biomarkers will be assessed on 3T and scored according to the STRIVE criteria.²⁰ White matter integrity will be assessed using quantitative MR measurements and perfusion will be assessed.

Biomarkers in blood and CSF

Blood samples will be analyzed for coagulation profiles, cholesterol levels, APOE status, inflammation profile and hormone levels. In addition, extra blood will be stored in the LUMC Biobank sCAA Neurological Diseases for future biomarker studies. Concentrations of A β 40, A β 42, t-tau, and p-tau181 will be measured in CSF and other biomarkers that may be identified in the future.

Other study parameters

Further parameters of this study will include demographic data, current medical conditions, vascular risk factors (including smoking, alcohol use, drugs, physical exercise, sleep, hypertension, hypercholesterolemia, diabetes mellitus, family history and medication; in women also information on female medical history such as number of pregnancies, menstruation cycle and menopause will be retrieved), neurologic history (including previous ischemic or hemorrhagic stroke), BMI, and blood pressure.

6.2 Study procedures

Data will be collected at four measuring points: at baseline, after three months, after six months and after 12 months:

- **Baseline (during admission or at the outpatient clinic < 1 month after ICH onset)**
Intake, baseline characteristics and neurological examination will be performed, as well as neuropsychological testing, blood sample collection, and a 3Tesla MRI scan. Additionally participants will be asked to undergo a lumbar puncture.
- **Three months (regular follow-up visit)**
At three months during the routine outpatient clinic visit a neurological examination will be performed, as well as neuropsychological testing.
- **Six and twelve months (two additional study visits)**
At six and twelve months, neurological examination will be performed, as well as neuropsychological testing, and a 3Tesla MRI scan. Additionally, participants will be asked to undergo a lumbar puncture.

• Intake, baseline characteristics and neurological examination

During the baseline assessment the following demographic and base line characteristics will be recorded: date of birth, gender, current medical conditions, daily intake alcohol/drugs/caffeine, sleep, physical activity, smoking, medication, cardiovascular risk factors and neurologic history (including previous ischemic or hemorrhagic stroke and history of migraine). In women information about menstruation cycle, pregnancies and menopause will be recorded. BMI will be recorded. Contra-indications for MRI will be checked. A standard neurological examination will be performed.

• Neuropsychological testing

As mentioned in 6.1, cognitive function will be tested using a Mini-Mental State Examination (MMSE), a Montreal Cognitive Assessment (MOCA), a Frontal Assessment Battery (FAB), Digit Span Test (DST), RAVLT-15 words test, Stroop test, Trail making test, the Hospital Anxiety and Depression Scale (HADS), the Center for Epidemiologic Studies Depression Scale (CES-D), the Neuropsychiatric Inventory Questionnaire (NPI-Q), the Starkstein Apathy Scale (SAS) and the Prikkelbaarheidsschaal (PS).

• 3Tesla MRI

MRI is a non-invasive method, which is able to detect abnormalities in the brain with a high resolution. MRI will be performed on a 3Tesla MR system. MR scanning is harmless to the health of the participant, for the scans in this protocol no contrast agents will be used. Scans are made by a certified MRI operator, who will accompany the participant and will check any MR contraindication. Scanning time will be kept to a maximum of 60 minutes for the complete protocol.

The following 3Tesla scan protocol will be used:

- Anatomical T1-weighted imaging
- T2-weighted imaging
- Fluid Attenuation Inversion Recovery (FLAIR)
- A Susceptibility Weighted Imaging (SWI)
- Diffusion-weighted imaging (DWI)
- Diffusion tensor Imaging (DTI)
- Arterial Spin Labeling (ASL)
- Post-gadolinium 3DT1 and 3DFLAIR

The 3T MRIs will be performed at inclusion and will be repeated at 6 months and after 1 year. The MRIs will be used to search for SVD markers (paragraph 6.1).

3T MRI's performed in the clinical setting can be used for study purposes with the participants permission. When a 3T is performed for research purposes only, participants generally will not receive the MRI results unless they want to know their personal outcome. In this case the results will be discussed with them by one of the neurologists/neurology residents.

• **Blood sample collection**

Blood samples (50 ml) will be analyzed for laboratory tests such as APOE status, cholesterol levels, inflammation and coagulation profile and hormone levels.

If participants give permission for LUMC Biobank sCAA (part of the LUMC Biobank Neurological Diseases), an additional 50 ml blood will be drawn. These blood samples will be stored for future (yet unknown) biomarker analysis after approval of the participants. These blood samples will be handled confidentially and coded and will be stored in the LUMC Biobank sCAA Neurological Diseases. The regulations of the LUMC Biobank Neurological Diseases will be applicable to the LUMC Biobank sCAA under Neurological Diseases

• **CSF sample collection**

The earlier mentioned contraindications (see paragraph 5.3) to lumbar puncture will be checked. CSF will be sampled by lumbar puncture under standardized conditions by experienced physicians. The lumbar puncture will be performed in the interspaces between the lumbar vertebrae, at the L3-S1 level, below the level where the spinal cord typically ends (L1) in adults. The lumbar puncture will be performed with sterile materials. The duration of the lumbar puncture is about 10 minutes. Atraumatic spinal needles will be used to minimize chances of post lumbar puncture headache. If a lumbar puncture fails with an atraumatic needle, a traumatic needle may be used.

In total approximately 20 ml CSF will be collected. For routine parameters, cell count, protein and glucose, a maximum of 8ml will be collected. CSF for the proposed biomarker assays (paragraph 6.1) will be collected in polypropylene tubes, centrifuged, divided into 0.5 ml aliquots, and stored at -80°C until analysis.

If participants give permission, additional CSF (12 ml) will be stored for future (yet unknown) biomarkers. By giving permission for CSF withdrawal and the LUMC Biobank sCAA Neurological Diseases, the subject gives permission for withdrawal and storing the CSF and coded medical information into the LUMC Biobank sCAA Neurological Diseases, which can be used for other scientific studies on biomarkers related to CAA without being notified. The regulations of the LUMC Biobank Neurological Diseases will be applicable to the LUMC Biobank sCAA Neurological Diseases.

Three days after the visit, subjects will be contacted to check whether the lumbar puncture has resulted in any persistent complaints. Subject will not receive the CSF results because the lumbar puncture will be performed for research purposes only.

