9.3 Benefits and risks assessment, group relatedness

To learn more about the pathophysiology, progression and prognosis of cognitive decline after ICH, we need to investigate ICH patients over a long period of time. By investigating MRI markers, CSF markers and cognitive functioning we will obtain more insight on individuals at risk. Moreover, this study hopefully eventually leads to new targets for therapy and will give insight in the sample size needed for a larger study to investigate mechanisms behind cognitive decline after ICH. Patients will

be informed extensively about the potential risks of the study procedures, after which written informed consent will be obtained.

The potential risks of this study are limited. The risks of gadolinium enhanced 3Tesla MRI are minimal. Gadolinium enhanced 3T MRI is performed in patients with ICH in routine clinical practice as part of the workup to find an underlying cause such as a tumor or a macrovascular cause according to the guidelines of the American Heart Association (2015) and the European Stroke Organisation (2019). Deposits of gadolinium can remain in the brains of some patients who have undergone 4 or more MRI scans with gadolinium for a prolonged time after the last administration. Deposits of gadolinium have also been reported in skin and bone. The European Medicines Agency has concluded that there is no evidence that gadolinium deposition in the brain has caused any harm to patients. A nephrogenic systemic fibrosis (NSF) has also been reported after gadolinium-based contrast agent administration. The most important risk factor for NSF is a severely reduced kidney function ($eGFR < 30 \text{ ml/min/1.73m}^2$). The type of gadolinium-based contrast agent is also determinant for the risk of NSF. Allergic reactions to gadolinium-based contrast agents have also been reported. Other potential risks include movement of ferromagnetic objects in the body. Some participants may feel claustrophobic in the restricted space of the MR scanner.

The potential risks related to MRI will be minimized in the following manner:

- Claustrophobia

Claustrophobia from the MRI scan will be reduced by explaining the nature of the scanner in detail before enrolment. At all times, the subjects will be able to communicate with the researcher, so if claustrophobia becomes a problem the subject can request to be removed from the scanner.

- Movement of ferromagnetic objects in the body

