A list of questions concerning risk factors of MRI must be filled in by the subject. Based on the answers the subject is or is not allowed to go into the scanner.

- Gadolinium will be administered once, the administered dose of gadolinium will be kept as low as possible, and a macrocyclic gadolinium-based contrast agent (Gadoteraat (Dotarem 0,5 mmol/ml, Guerbet) will be used to maximize safety. After administering gadolinium participants will be under observation for at least 30 minutes to check on signs of an allergic reaction. Participants will be advised to avoid repeated gadolinium administering in the next 24hours and creatinine clearance will be checked for reduces kidney function.

Blood withdrawal via venous puncture in the elbow has a very low rate of adverse events. The needle puncture may cause bruising and in very rare cases an infection of the skin or blood vessel may occur at the puncture site.

A lumbar puncture is a minimal burdening to patients if the patient is in the right position and if the patient has a normal anatomy of the vertebrae. Usually, the lumbar puncture itself takes about 10 minutes and patients stay in the hospital afterwards for about half an hour. The most frequently occurring complication of lumbar puncture is post-lumbar puncture headache. This complication is much rarer when atraumatic spinal needles are used. If post-lumbar puncture headache occurs, subjects should take bed rest, drink ample water, and may use paracetamol if required. If the post-

lumbar puncture headache persists for more than a week, a blood patch may be considered which is usually effective in treating the headache.^{21, 22} Very rarely, infection such as meningitis or spinal abscess may occur. Patients will be contacted by phone three days after lumbar puncture to check whether the lumbar puncture has resulted in any persistent complaints. If there are complaints following the puncture, one of the neurologists will contact the patient to make sure adequate measures (e.g. a blood patch) are taken.

The potential risks related to lumbar puncture will be minimized in the following manner:

- Post-lumbar puncture headaches

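### Section 6.2 says no contrast agent is used, yet its own scan list includes post-gadolinium sequences, and no section names the visit for the single dose stated in 9.3

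*Protocol*

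**What the plan says.** Protocol section 6.2, under 3Tesla MRI, calls scanning harmless and says that "for the scans in this protocol no contrast agents will be used". The scan protocol that follows in the same subsection ends with "Post-gadolinium 3DT1 and 3DFLAIR". It is a single list, not divided by visit. The timing is given after it: "The 3T MRIs will be performed at inclusion and will be repeated at 6 months and after 1 year".

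Section 9.3 treats the study MRI as gadolinium enhanced. It describes tissue deposits, nephrogenic systemic fibrosis and allergic reactions, then lists measures to reduce MRI risk. Among these are a named macrocyclic agent, the lowest possible dose, at least 30 minutes of observation, a creatinine clearance check, and the statement "Gadolinium will be administered once". It also places contrast MRI in ordinary care: "Gadolinium enhanced 3T MRI is performed in patients with ICH in routine clinical practice".

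Among the MRI contraindications, section 5.3 lists severely reduced kidney function and a previous reaction to gadolinium. The Summary rates MRI risk as minimal on the ground that participants' health is unaffected, and does not mention contrast.

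**The concern.** Two statements a few lines apart in the procedures section cannot both be true: either contrast is given in this study or it is not. Section 6.2 also places its claim of harmlessness in the same sentence as the absence of contrast, so an error about contrast undermines that risk statement too.

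The second problem is the number and timing of doses. With three study MRIs and one undivided scan list, someone following 6.2 would acquire the post-gadolinium sequences every time. Someone following 9.3 would give one dose but would not know at which visit. What is at stake is each participant's exposure to an injected agent, and whether the protocol describes that exposure and its risks consistently.

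**Working it through.** No statistical formula applies. The check sets the statements side by side and counts doses.

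**Step 1: is contrast planned?**

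| Place | What it implies |
|---|---|
| 6.2, sentence on contrast | No gadolinium at any study scan |
| 6.2, scan list | Gadolinium is given |
| 5.3, MRI contraindications | Gadolinium is given (renal and allergy exclusions) |
| 9.3, risks and precautions | Gadolinium is given (agent named, observation period, creatinine check) |

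Three places agree and one sentence disagrees with all of them. Gadolinium is intended, and the 6.2 sentence is the error.

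**Step 2: how many doses?**

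Doses per participant completing all visits = number of study MRIs at which the post-gadolinium sequences are run. Section 6.2 gives three study MRIs (inclusion, 6 months, 12 months).

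- 6.2 sentence taken literally: 0 of 3 MRIs, so 0 doses.
- 9.3, with once meaning once per participant: 1 of 3 MRIs, so 1 dose.
- 6.2 list run as written at every MRI: 3 of 3 MRIs, so 3 doses.

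The figure in 9.3 is reproduced only if the sequences are confined to one visit, and 6.2 does not confine them.

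**Step 3: which reading of 9.3 is better supported?**

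The statement stands among the measures meant to keep MRI risk low, next to the instruction to use the lowest dose. That favours one dose per participant. The remark about routine work-up of ICH ("Gadolinium enhanced 3T MRI is performed in patients with ICH in routine clinical practice") suggests the baseline scan. Against this, 9.3 also advises participants to avoid further gadolinium for 24 hours, which is advice about a single session and leaves a once-per-scan meaning just possible. No section names the visit.

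**Step 4: does the conflict disappear with a text change?**

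If the no-contrast sentence is removed and the sequences are limited to one named visit, the count is 1 in both 6.2 and 9.3, and 5.3 needs no change.

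**The case against.** The strongest reply is that the document resolves itself. Every other relevant passage assumes gadolinium, so the 6.2 sentence is an uncorrected remnant rather than an open design question. On the count, 9.3 gives a specific number, and a specific statement normally governs a general list that is silent on visits. Much of this stands. It settles what was meant about contrast, and it makes one dose per participant the better reading. It does not make the 6.2 sentence correct, and it does not supply the missing visit.

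A reader might infer more than the text supports:

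- **That three doses are planned, or that participants are pushed towards the deposition risk.** Section 9.3 mentions deposits in some "patients who have undergone 4 or more MRI scans with gadolinium", but as an observation and not as a dosing limit. It adds that the European Medicines Agency found no evidence of harm from brain deposits. Neither one nor three study doses reaches that number alone. Section 6.2 also allows clinical 3T scans to be used with permission, so a baseline contrast scan may be one the patient would have had anyway.
- **That renal safety is unguarded.** Section 5.3 lists "Reduced kidney function (estimated GFR < 30" ml/min/1.73 m²) as a contraindication, 6.2 has a certified operator "who will accompany the participant and will check any MR contraindication", and 9.3 foresees a creatinine clearance check. The exact laboratory window is operational detail.
- **That participants are misinformed.** The information letter is not among the documents, and 9.3 says that the risks will be explained extensively.
- **That the Summary is wholly wrong.** Section 9.3 also rates the risk of contrast MRI as minimal. Only the Summary's reason, that health is unaffected, goes too far.

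**Conclusion.** The no-contrast sentence in 6.2 is wrong as written. This needs no assumption, because the contradiction lies within one subsection and sections 5.3 and 9.3 show which side is intended. The dose count is a weaker point: an ambiguity between 6.2 and 9.3. One dose per participant is the natural meaning, probably at baseline, but the visit is nowhere stated, and running the 6.2 list at each MRI would give three. The range of 1 to 3 assumes a participant who completes all three MRIs and counts only doses given at study scans.

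This should be fixed, but it is not a defect that invalidates the study. It concerns participant safety and the description of risk. No endpoint, sample size or analysis depends on it.

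**What to change.** 1. In 6.2, delete the sentence that calls scanning harmless and denies the use of contrast.
2. In the 6.2 scan list, limit the post-gadolinium sequences to the intended visit. If once means per study, as seems likely, label them as acquired at the baseline MRI only, one dose per participant.
3. In 9.3, state the same visit and the same dose count. If the sponsor does mean once per scan, both sections should say so and give the total of three.
4. In the Summary, remove the clause that justifies minimal MRI risk by an absence of health consequences, or align it with the gadolinium risks in 9.3.

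The exclusions in 5.3 stay as they are. The cost is a wording amendment notified to the ethics committee under section 10.3. With a single baseline dose there are no post-gadolinium images at 6 and 12 months, but section 6.1 ties no named marker to those sequences. There is no statistical cost.

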6.3 Withdrawal of individual subjects

Subjects can leave the study at any time for any reason if they wish to do so without any consequences. The investigator can decide to withdraw a subject from the study for urgent medical reasons. Decision to leave the study will not influence the diagnostic trajectory or treatment of patients in any way. In case a participant becomes mentally incompetent during the study period, the participant continues with the study unless he/she desires to end the participation or shows (verbal or non-verbal) resistance to the study procedures.

6.4 Replacement of individual subjects after withdrawal

Individual subjects who withdraw from the study or die before the end of the study will be replaced. The reason of withdrawal will be asked, but participants are also ensured that they don't need to give a reason for ending their participation. Replaced individuals will not be excluded from the analysis.

